5.2.1. Study duration

The duration of the study for each participant is expected to be ~ 8 weeks.

5.3. Study endpoints

5.3.1. Primary endpoints

1. Pain relief at 2 hours post-treatment:

The proportion of participants achieving pain relief at 2 hours post-treatment in the test treatment, with no use of rescue/abortive medication (Pain relief defined as a reduction in pain scale from severe to moderate, mild, or none)from moderate or severe to mild or none.

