	3. Participants with epilepsy.4. Participants who have undergone nerve block (occipital or other) in the	
	head or neck, or treatment with onabotulinum toxin A (Botox) to the head	
	and/or neck in the prior four months.	
	5. Current participation in any other clinical interventional study	
	Participants without basic cognitive and motor skills required for operating a smartphone.	
	7. Pregnant or breastfeeding females	
	8. Participants who have previous experience with the device	
	9. Participants with arm circumference below 7.9 inches (20 cm)	
Study Design	A prospective, single arm, open label trial.	
	The study will be conducted in two phases:	

Revision #: 1.0

Page: 6 of 20

	Phase I - Run-in: Eligible participants will use a smartphone headache diary application for 28 days. Participants who report at least 22 entries (70%) AND a constant and unremitting headache will be included in the treatment phase. The C-SSRS will be administered at the screening visit and a "since last visit" form which will be administered at each subsequent in-clinic study visit to assess possible suicidal ideation and behavior. The C-SSRS will be scored by the investigator or Study Coordinator who has C-SSRS certification. The survey will be scored immediately after taken by participant. If reports of suicidal ideation with intent to act (endorse item 4 or 5), reports of actual, aborted, or interrupted suicide attempts, or reports of behavior preparatory for an attempt are identified, the investigator" will refer the subject for further examination. Phase II - Treatment phase: Participants who meet the run-in requirements will receive an active Nerivio device. Participants will be instructed to use the device within 60 minutes of awakening with a headache or upon increasing headache severityduring a period of 4 week. A treatment session is of 45 minutes The participants will use the app to record pain intensity levels at baseline and 2-hours post-treatment, and to record the presence/absence of associated	
Qualifying NDHP attack	A qualifying NDPH attack is defined as a headache that: 1. is at an intensity above their baseline pain 2. is present upon awakening	
Primary endpoint	Pain relief at 2 hours post-treatment: The proportion of participants achieving pain relief at 2 hours post-treatment in the test treatment, with no use of rescue/abortive medication (Pain relief defined as a reduction from severe to moderate, mild or none, moderate to mild or none, or mild to none)	

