During the training, participants will also be informed on the key elements which are critical for the successful conduct of the study:

Revision #: 1.0 Page: 13 of 20

- Treatments of headache with Nerivio[™] should be performed within 60 minutes of awakening with a headache or upon increasing headache severity and always within one hour of symptoms onset. Treatments of mild headaches are accepted.
- Avoid taking rescue medications within two hours post-treatment (2 hours from start of treatment), if possible.

Revision #: 1.0

Page: 14 of 20

• The treatment should be performed for 45 minutes.

In addition, participants will complete study questionnaires, as required.

Phase 2 – Treatment phase: Participants will be instructed to use the device within 60 minutes of awakening with a headache or upon increasing headache severity during a period of 4 week. Participants will be instructed to use the device with the intensity level identified during the device training visit (with a range of ±5 units) and make sure the stimulation is perceptible but not painful. Participants will be instructed to avoid taking rescue medications within 2 hours post-treatment. If medications are used, participants will be instructed to record in the app when and which medication was taken. The participants will use the app to record pain intensity levels (none, mild, moderate, or severe) at baseline and 2 hours post-treatment, and to record the presence/absence of associated symptoms (nausea, photophobia, phonophobia) at baseline and 2 hours post-treatment.

Participants who do not achieve satisfactory relief at 2 hours post-treatment may treat again with the Nerivio[™] device or may treat with usual care at that time or any time thereafter if the headache does not resolve.

Third (final) visit – End of study: Participants will return to the clinic following the end of the 4-week treatment phase, at which time they will return the device and complete the required questionnaires

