5.3.2. Secondary endpoints

1. Within-patient consistency

The repeatability of headache reduction, as described in the primary endpoint definition, in subsequent treated attacks. Thus, this endpoint measures the %

Revision #: 1.0

Page: 15 of 20

of patient responding to the primary endpoint in at least 50% of their treated attacks.

2. Disappearance of associated symptoms at 2 hours post-treatment

Disappearance of nausea, photophobia and phonophobia at 2 hours post-treatment.

3. Functional disability at 2 hours post-treatment

The proportion of participants achieving improvement of at least one grade in functional disability in the test treatment at 2 hours post-treatment with no use of rescue medication.

4. Improve of quality of life

Reduction in average headache disability as measured by PedsMIDAS before and at 1 month after initiation of treatment with REN.

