6.4.4. Efficacy analysis

The efficacy endpoints will be assessed on evaluable treatments of qualifying attacks. The first use of the device is considered a training treatment and will not be included in the efficacy analyses. The first treatment of a qualifying attack after the training treatment is considered a test treatment and will be used for all efficacy assessments. If this treatment is not evaluable (i.e., no pain data at 2 hours post-treatment), a subsequent treatment of a qualifying attack with evaluable data will be considered the test treatment.

Use of rescue medication before the 2-hours assessment will be considered a treatment failure for the 2-hours endpoints, and before the 24 hours assessment for the sustained 24-hours endpoints. The percentage of participants achieving each of the efficacy outcomes will be presented in a tabular form along with two-sided 95% exact confidence intervals.

For the associated symptoms outcomes, the observed response proportions and corresponding 95% exact confidence intervals for each associated symptom will be provided. All patients with baseline and 2 hours values will be included in the analyses. A response in each associated symptom (nausea, vomiting, photophobia, phonophobia) is defined as change from presence of a specific associated symptom at baseline to absence of the same associated symptom at 2 hours post-treatment.

In addition, logistic regression models will be used to assess the efficacy. Baseline value and site will serve as covariates.

The first secondary endpoint (pain relief at 2 hours) may also be evaluated in attacks with aura and attacks without aura separately.

7. Data management

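### The synopsis and section 5.3.1 define pain relief at 2 hours differently, so the primary proportion has no unique value

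*Combined protocol and SAP*

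**What the plan says.** The primary endpoint is the proportion of participants with pain relief 2 hours after the test treatment, without rescue medication. Relief is defined in two places.

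- Synopsis, Primary endpoint: "Pain relief defined as a reduction from severe to moderate, mild or none, moderate to mild or none, or mild to none".
- Section 5.3.1: "Pain relief defined as a reduction in pain scale from severe to moderate, mild, or none)from moderate or severe to mild or none".

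Other text that bears on the rule:

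- Section 5.2 has participants "record pain intensity levels (none, mild, moderate, or severe) at baseline and 2 hours post-treatment", so the scale has four grades. It also states "Treatments of mild headaches are accepted".
- The synopsis defines a qualifying attack as one that, among other things, "is at an intensity above their baseline pain".
- Section 6.4.4 selects the treatment to analyse: "The first treatment of a qualifying attack after the training treatment is considered a test treatment and will be used for all efficacy assessments". It does not define relief. It refers to pain relief at 2 hours under a secondary label: "The first secondary endpoint (pain relief at 2 hours) may also be evaluated".
- Section 5.3.2 carries the primary definition into within-patient consistency: "The repeatability of headache reduction, as described in the primary endpoint definition, in subsequent treated attacks".
- Section 6.3 makes the mITT set primary for efficacy. None of its sets is restricted by starting pain grade.

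**The concern.** The two definitions classify the same participant differently. A participant who goes from severe to moderate responds under the synopsis and under the bracket in 5.3.1, but not under the words after the bracket. A participant who goes from mild to none responds under the synopsis only. No passage says which text governs, or whether a treatment that starts at mild stays in the denominator.

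The plan has no comparator, hypothesis test, benchmark or sample size calculation. The proportion and its exact 95% interval are therefore the main efficacy result. The harm is to what is estimated, not to error rates or power. In an open-label single-arm study, a rule left open can be settled once responses are known. The consistency endpoint inherits the same ambiguity.

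**Working it through.** The plan states no expected response rate, so there is no figure to reproduce.

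**Step 1. Which improvements count.** A four-grade scale allows six improvements.

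| Change | Synopsis | 5.3.1, both parts | 5.3.1, text after bracket | 5.3.1, bracket only |
|---|---|---|---|---|
| Severe to moderate | yes | yes | no | yes |
| Severe to mild | yes | yes | yes | yes |
| Severe to none | yes | yes | yes | yes |
| Moderate to mild | yes | yes | yes | no |
| Moderate to none | yes | yes | yes | no |
| Mild to none | yes | no | no | no |
| Total | 6 | 5 | 4 | 3 |

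No column for 5.3.1 equals the synopsis.

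**Step 2. Size of the gap.** Let *s* and *m* be the shares of test treatments starting at severe and at mild, *a* = P(severe to moderate) and *b* = P(mild to none). With the same denominator throughout:

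- synopsis minus trailing rule = *s* × *a* + *m* × *b*
- synopsis minus both parts of 5.3.1 = *m* × *b*

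The documents give none of these quantities, so all are assumed. With no mild starts (*m* = 0), the first gap in percentage points is:

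| Severe share *s* | *a* = 10% | *a* = 30% | *a* = 40% |
|---|---|---|---|
| 0% | 0 | 0 | 0 |
| 10% | 1 | 3 | 4 |
| 30% | 3 | 9 | 12 |
| 50% | 5 | 15 | 20 |

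**Step 3. One assumed data set under each reading.** Assume 30 severe starts (9 to moderate, 6 to mild or none), 50 moderate starts (20 to mild or none) and 20 mild starts (6 to none). The intervals are exact (Clopper-Pearson) two-sided 95%.

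| Rule | No mild starts, N = 80 | With 20 mild starts, N = 100 |
|---|---|---|
| Synopsis | 9 + 6 + 20 = 35; 43.8% (32.7–55.3) | 35 + 6 = 41; 41% (31.3–51.3) |
| 5.3.1, both parts | 35; 43.8% (32.7–55.3) | 35; 35% (25.7–45.2) |
| 5.3.1, text after bracket | 6 + 20 = 26; 32.5% (22.4–43.9) | 26; 26% (17.7–35.7) |
| 5.3.1, bracket only | 9 + 6 = 15; 18.8% (10.9–29.0) | 15; 15% (8.6–23.5) |

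The formula agrees. Without mild starts, the gap between synopsis and trailing rule is (30/80) × 0.30 = 11.25 points (43.75 − 32.5). With mild starts it is 0.30 × 0.30 + 0.20 × 0.30 = 15 points (41 − 26).

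**Step 4. Within-patient consistency.** Take a participant with four treated attacks: two severe to moderate, one moderate to mild, one unchanged. The synopsis rule gives 3/4 = 75% and the trailing rule 1/4 = 25%. The 50% cut-off lies between them.

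**The case against.** The strongest reply is that mild starts will be rare in the primary analysis. Efficacy is assessed on qualifying attacks, which must exceed the participant's own baseline pain, and entry to treatment requires a continuous headache. If that baseline is graded on the same four-grade scale, it is at least mild and a qualifying attack is at least moderate. The synopsis and the combined reading of 5.3.1 then agree (35/80 each above), and a conflict remains only if one part of 5.3.1 is read alone.

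Much of this stands. The no-mild column is the more relevant one, and the sentence accepting mild headaches concerns device use, not the choice of test treatment. But the scale for baseline pain is not stated, so mild starts are unlikely rather than excluded. The same argument also makes the other disputed change more likely. On that scale, a participant with constant moderate pain can qualify only at severe, and a return to the usual level is then severe to moderate.

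The broken sentence may be an editing remnant. That does not settle the rule, since keeping either part alone still departs from the synopsis.

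It is also fair to say that the rates are assumed, that the consistency example shows possibility rather than likelihood, and that every version can be tabulated from grades already recorded. Tabulating all versions does not say which one is primary. The secondary label in 6.4.4 is a separate slip and does not itself show that the responder rule is ambiguous.

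**Conclusion.** The concern holds and needs correction before analysis. The current text defines the sole primary efficacy endpoint in ways that cannot be reconciled, and 6.4.4 does not choose between them.

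The contradiction rests on the text alone. Its numerical size does not. Without mild starts, severe shares of 0% to 50% and P(severe to moderate) of 10% to 40% put the gap between the synopsis and the trailing rule at 0 to 20 points. It is nil if all test treatments start at moderate. If both parts of 5.3.1 apply and none start at mild, 5.3.1 and the synopsis give the same result. The bracket read alone departs furthest in the assumed data.

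**What to change.** Before outcome data are reviewed:

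1. Put one responder rule, identically worded, in the synopsis and 5.3.1, and have 6.4.4 refer to it. The synopsis rule (at least one grade lower at 2 hours, no rescue medication) is workable: it is complete, and every permitted treatment can respond. Its drawback is that it is the most lenient version. A rule limited to moderate or severe starts also works if the denominator is limited in the same way.
2. State whether test treatments that start at mild are in the denominator, and on what scale the baseline pain in the qualifying-attack definition is graded.
3. If the synopsis rule is kept, name one sensitivity analysis: moderate or severe to mild or none, among moderate or severe starts only.
4. In 6.4.4, call pain relief at 2 hours the primary endpoint.

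The cost is wording in three places and one extra table. No new data are needed, because pain grade is already recorded at baseline and at 2 hours.

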5.3.2. Secondary endpoints

1. Within-patient consistency

The repeatability of headache reduction, as described in the primary endpoint definition, in subsequent treated attacks. Thus, this endpoint measures the %

Revision #: 1.0

Page: 15 of 20

of patient responding to the primary endpoint in at least 50% of their treated attacks.

2. Disappearance of associated symptoms at 2 hours post-treatment

Disappearance of nausea, photophobia and phonophobia at 2 hours post-treatment.

3. Functional disability at 2 hours post-treatment

The proportion of participants achieving improvement of at least one grade in functional disability in the test treatment at 2 hours post-treatment with no use of rescue medication.

4. Improve of quality of life

Reduction in average headache disability as measured by PedsMIDAS before and at 1 month after initiation of treatment with REN.

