
Revision #: 1.0

Page: 7 of 20

Within-patient consistency

The repeatability of headache reduction, as described in the primary endpoint definition, in subsequent treated attacks. Thus, this endpoint measures the % of patient responding to the primary endpoint in at least 50% of their treated attacks

Disappearance of associated symptoms at 2 hours post-treatment

Disappearance of nausea, photophobia and phonophobia at 2 hours post-treatment

Functional disability at 2 hours post-treatment

The proportion of participants achieving improvement of at least one grade in functional disability in the test treatment at 2 hours post-treatment with no use of rescue medication

Improve of quality of life

Reduction in average headache disability as measured by PedsMIDAS before and at 1 month after initiation of treatment with REN.

Revision #: 1.0 Page: 8 of 20

Exploratory endpoints	 Reduction in average headache intensity at 1 month after initiation of treatment with REN Reduction in perceived stress as it relates to headache, and adverse reactions experienced as measured by HIT-6.
Safety endpoints	 The safety of Nerivio The incidence of adverse events in general and by seriousness, severity and association to the device. Treatment tolerability The percent of subjects who fail to complete the study because of adverse events
Datasets	 Intent to treat analysis set (ITT) The ITT analysis set includes all participants undergoing the treatment phase. Modified intent to treat analysis set (mITT) The mITT analysis set includes all participants undergoing the treatment phase who treat a test treatment within 60 minutes of attack onset.
Data Analysis	The ITT analysis set will be used for the primary endpoints of safety and tolerability assessments. Safety assessments will include spontaneously reported adverse events. The mITT analysis set will be used for the efficacy assessments.

Revision #: 1.0

Page: 9 of 20

2. Background

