6.3. Analysis sets

Intent to treat analysis set (ITT)

The ITT analysis set includes all patients undergoing the treatment phase.

Modified intend to treat analysis set (mITT)

The mITT analysis set includes all patients undergoing the treatment phase and treat at least one (1) treatment within 60 minutes of headache onset. Subjects with no valid post baseline assessment will not be included in the relevant analysis.

Per-protocol analysis set (PP)

The PP analysis set includes all patients from the mITT analysis set without major protocol deviations. Main protocol instructions include:

- has started within 60 minutes of awakening with headache or increased intensity from baseline
 - was administered for 45 minutes
 - includes data on headache intensity at 2 hours post-treatment
 - rescue medication was not used before or within 2 hours post-treatment

Statistical analysis of the analysis sets

The ITT analysis set will serve as the main set for safety assessments.

The mITT analysis set will serve as the primary set for the efficacy assessment.

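### Within-patient consistency sets no minimum number of attacks and lets a tie pass, so its percentage depends on attack counts as well as on repeatability

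*Combined protocol and SAP*

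**What the plan says.** The Synopsis and section 5.3.2 give within-patient consistency as the first secondary endpoint. The concept is stated as "The repeatability of headache reduction, as described in the primary endpoint definition, in subsequent treated attacks". The measure is the percentage of patients "responding to the primary endpoint in at least 50% of their treated attacks".

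Neither place sets a minimum number of attacks. The only floor is in section 6.3, where the mITT (efficacy) set takes patients who "treat at least one (1) treatment within 60 minutes of headache onset".

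Section 6.4.4 adds two rules. On training: "The first use of the device is considered a training treatment and will not be included in the efficacy analyses". The first qualifying attack treated after that "is considered a test treatment and will be used for all efficacy assessments". Results are reported as percentages with exact two-sided 95% confidence intervals. Nothing is said about participants who contribute different numbers of attacks.

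**The concern.** An endpoint named for repeatability should need at least one opportunity to repeat. As worded, this one does not.

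- With one treated attack, a responder scores 1/1 and passes, which adds nothing to a single-attack response.
- With two, a single response scores 1/2 and passes on the tie.

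Because ties pass, even attack counts have an advantage over neighbouring odd counts at the same response rate. As the count grows, the chance of passing also drifts towards 0 or 1, depending on whether the response rate is below or above one half.

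Two cohorts with the same per-attack response could therefore report different consistency percentages only because they treated different numbers of attacks. Counts are likely to vary. A qualifying attack in the Synopsis "is at an intensity above their baseline pain" and is there on waking, and use is self-directed over four weeks. The exact interval conveys sampling error, not this dependence.

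The set of attacks is also not pinned down. The word in "in subsequent treated attacks" may or may not leave out the test treatment. Section 5.2 allows a second session if relief is unsatisfactory, without saying that it belongs to the same attack.

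**Working it through.** The plan gives no expected consistency rate, power or attack count, so there is no figure of its own to reproduce. The check is of how the rule behaves.

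**Inputs from the plan.** Threshold: at least half of n attacks, that is at least ceil(n/2) responses. Minimum n: none stated. Treatment period: 4 weeks (section 5.2).

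**Assumptions, not in the documents.** Per-attack response probability p from 0.2 to 0.8. Intraclass correlation (ICC) within participant of 0, 0.2 or 0.5. With at most one treated attack a day and the first use spent on training, n runs from 1 to 28 − 1 = 27.

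**Formula.** With independent attacks, P(consistent | n, p) = P(X ≥ ceil(n/2)), X ~ Binomial(n, p). With correlation, X is beta-binomial with a = p(1/ICC − 1) and b = (1 − p)(1/ICC − 1).

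**Worked values at p = 0.4, independent.**
- n = 1: 0.4
- n = 2: 1 − 0.6² = 0.64
- n = 3: 3(0.4²)(0.6) + 0.4³ = 0.288 + 0.064 = 0.352
- n = 4: 1 − 0.6⁴ − 4(0.4)(0.6³) = 1 − 0.1296 − 0.3456 = 0.5248
- n = 5: 0.2304 + 0.0768 + 0.0102 = 0.317

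| p | ICC | n=1 | n=2 | n=3 | n=4 | n=5 | n=20 |
|---|---|---|---|---|---|---|---|
| 0.2 | 0 | 0.200 | 0.360 | 0.104 | 0.181 | 0.058 | 0.003 |
| 0.3 | 0 | 0.300 | 0.510 | 0.216 | 0.348 | 0.163 | 0.048 |
| 0.4 | 0 | 0.400 | 0.640 | 0.352 | 0.525 | 0.317 | 0.245 |
| 0.5 | 0 | 0.500 | 0.750 | 0.500 | 0.688 | 0.500 | 0.588 |
| 0.6 | 0 | 0.600 | 0.840 | 0.648 | 0.821 | 0.683 | 0.872 |
| 0.7 | 0 | 0.700 | 0.910 | 0.784 | 0.916 | 0.837 | 0.983 |
| 0.8 | 0 | 0.800 | 0.960 | 0.896 | 0.973 | 0.942 | 0.999 |
| 0.3 | 0.2 | 0.300 | 0.468 | 0.255 | 0.356 | 0.235 | 0.224 |
| 0.3 | 0.5 | 0.300 | 0.405 | 0.286 | 0.344 | 0.281 | 0.288 |
| 0.4 | 0.2 | 0.400 | 0.592 | 0.374 | 0.496 | 0.362 | 0.371 |
| 0.4 | 0.5 | 0.400 | 0.520 | 0.392 | 0.459 | 0.389 | 0.400 |

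**How many passes at n = 2 lack a second response.** At p = 0.4, independent, both attacks respond with probability 0.4² = 0.16. So 0.64 − 0.16 = 0.48 pass on one response, which is 0.48/0.64 = 75% of those classed as consistent. At p = 0.3 with ICC 0.5, both respond with probability 0.3 × 1.3/2 = 0.195, and (0.405 − 0.195)/0.405 = 52%.

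**Effect of the attack mix.** At p = 0.3, independent, a cohort split equally between 1 and 2 attacks gives (0.300 + 0.510)/2 = 0.405. One split equally between 10 and 20 gives (0.150 + 0.048)/2 = 0.099. The per-attack response is the same in both.

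**A measure without this problem.** A participant's own proportion of responding attacks, X/n, has expectation np/n = p for any n. The mean of these proportions over participants therefore does not move with attack count when p is the same throughout.

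**The case against.** Several points on the other side are sound.

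- **Low counts may be rare.** The run-in admits only participants with constant headache, and treatment lasts four weeks, so many attacks each are plausible. At 20 independent attacks the rule separates p = 0.3 (0.048) from p = 0.7 (0.983). This stands as a limit on the point. But the plan gives no expected count and cannot rely on a high one.
- **Correlation dampens the swing.** At p = 0.3 and ICC 0.5, the range over 1 to 5 attacks is 0.281 to 0.405, against 0.163 to 0.510 with independence. It narrows but does not vanish.
- **The word subsequent may exclude one-attack participants.** It may, but the sentence that defines the percentage has no such limit. If only attacks after the test treatment count, one later attack with a response still passes as 1/1, whether or not the test treatment responded.
- **A repeat session is not a new attack.** The endpoint counts attacks, so this is the natural reading. Saying so is a clarification.
- **A two-attack minimum alone does not cure it.** Correct: n = 2 is where the tie matters most. At p = 0.4 with equal weights, the average over n = 1 to 5 is 2.234/5 = 0.447, and over n = 2 to 5 it is 1.834/4 = 0.459, slightly further from 0.4.

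A reader might also infer that section 6.4.4 makes the endpoint impossible to compute, since one treatment serves every efficacy assessment. The documents do not support that. The same section speaks of evaluable treatments in the plural, the endpoint's own definition refers to further attacks, and PedsMIDAS is not tied to a single treatment either. The sentence is too broad, not fatal.

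**Conclusion.** The point holds as a cheap improvement to a secondary endpoint. On the literal wording, participants can be classed as consistent with no repeated response, and the percentage mixes attack count with repeatability. Under independence, passing at two attacks rather than three differs by 0.510 − 0.216 = 0.29 at p = 0.3, and by 0.640 − 0.352 = 0.29 at p = 0.4. With ICC 0.5 the differences are about 0.12 and 0.13. All of these rest on assumed p, ICC and n.

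Three stronger readings are not supported. Not every one-attack participant counts as consistent, because 0/1 fails. It is not true that the rule does not measure repeatability: one attack carries no such information and two carry little, but many attacks do. Nor is the result beyond interpretation, since reporting the attack counts beside it would make it readable. No test or success criterion depends on this endpoint.

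**What to change.** In section 5.3.2 and the Synopsis:

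1. Restrict the endpoint to participants with at least two evaluable treated qualifying attacks after the training treatment, and report that denominator.
2. State whether the test treatment is one of the attacks counted.
3. Count one session per attack.

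In section 6.4.4:

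4. Tabulate the result by number of attacks, because the minimum alone leaves the tie effect at n = 2.
5. Report beside it the mean per-attack response probability, with participants weighted equally and a 95% confidence interval clustered on participant.
6. Limit the sentence on the single test treatment to the endpoints that are defined on it, so that it conflicts with neither consistency nor PedsMIDAS.

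The underlying response must be settled as well: the Synopsis counts mild to none as relief and section 5.3.1 does not list it, and the difference carries into this endpoint.

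The cost is wording, since the app already records the data. The one loss is that participants with a single evaluable attack leave this secondary endpoint.
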